In keeping with recommendations from an adolescent varenicline pharmacokinetic study (26), participants >55 kg will take varenicline/placebo 0.5 mg once daily for 3 days, titrated to 0.5 mg twice daily for 4 days, titrated to 1 mg twice daily thereafter. Participants ≤55 kg will take varenicline/placebo 0.5 mg once daily for 7 days, titrated to 0.5 mg twice daily thereafter. In our previous experience with varenicline within adolescents, most participants (80%) weighed enough to receive the 2 mg per day dosage.

During weekly visits, study personnel will review medication logs, inspect blister packs, and perform pill counts to monitor medication adherence. Participant compensation at medication visits will be, in part, contingent upon bringing in blister packs and completing medication logs. The study medical clinician

Pro00014398

(physician or physician assistant) will systematically assess medication tolerability and effects, including neuropsychiatric effects (see Section C3e below). Medication supply will be refreshed for ongoing use over the following week. Participants will be encouraged to contact the study medical clinician between visits to address any immediate concerns regarding adverse effects. The study medical clinician will be available "on call" at all times for evaluation and management of adverse events. If a participant experiences intolerable medication-related adverse effects at any point during the study, a dose reduction may be undertaken. If a participant is unable to tolerate the reduced dose, medication will be discontinued, and the participant will be encouraged to remain in the study for monitoring and non-medication study procedures.

Psychosocial Intervention

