Secondary outcomes include the following: a) 7-day biologically confirmed point prevalence abstinence at 6 months, b) continuous abstinence, c) time to lapse (first puff), d) time to relapse (first of 3 consecutive days smoking ≥ 1 cigarette), and e) longitudinal efficacy of varenicline. These will be tested via logistic regression to examine a) point prevalence at 6 months and b) continuous abstinence from targeted quit date (Week 1) to both treatment conclusion (Week 12) and final follow-up visit (Week 26), Cox Proportional hazard models (83) to examine c) time to first lapse (first puff, first cigarette), d) time to relapse (first of 3 consecutive days smoking ≥ 1 cigarette), and e) Generalized Estimating Equation (repeated measures) to examine the entire study time course. Repeated measures analysis of variance will be used to assess treatment effects of varenicline on craving (QSU-B), withdrawal (MNWS), and smoking reinforcement (mCEQ) throughout the study. All efficacy analyses (primary and secondary) will be repeated among participants with $\geq 80\%$ medication adherence, per protocol analysis, and completers analysis. Medication adherence (pill counts), nicotine dependence (mFTQ, AUTOS), motivation/readiness to quit (baseline rating), self-efficacy (GSES), perceived social support (MSPSS), and impulsivity (BIS-11) will be explored as possible moderators influencing the effect of varenicline on abstinence.

Safety: Secondary Analysis

Of particular interest will be adverse events leading to medication discontinuation and the occurrence of treatment-related serious adverse events (SAEs) (see Human Subjects Section 4.6). We will specifically compare neuropsychiatric adverse events (Psychiatric Interview) using non-inferiority testing, as well as depression/anxiety (HADS) and suicidality (C-SSRS) ratings using one-sided 2-sample t-tests. Based on adult literature (34,35), we anticipate no serious adverse events, and appropriate stopping plans are in place (see section C3g) for added precaution.

Participant Retention Analysis

Total number of treatment visits attended will be compared using a Student's *t*-test, while the number of days retained will be assessed using Cox Proportional Hazards regression models.

C3g. Clinical Management Issues

Study Termination

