Study termination may be initiated by a study participant (or parent/guardian, as applicable) for personal reasons, or by the PI or members of the Data Safety and Monitoring Board for reasons of participant safety or the additional requirement for more intensive or a different form of therapy for addiction, medical, or psychiatric disorders. Another cause for termination would be any participant behavior that is felt to present a threat or harm to staff, including sexual or verbal harassment. Other terminations may be due to a participant becoming lost to follow up and/or moving from the geographic area. Frequency counts for reasons for termination will be analyzed for both treatment groups using chi square analytic procedures. If a participant is terminated for any reason, attempts will be made to continue collecting adverse event and smoking data over the 12-week treatment trial and follow-up period so that data can be entered for the intent-to-treat analysis.

Clinical Deterioration "Rescue Plan"

A clinical deterioration "rescue" plan will be in place for participants that experience psychiatric or substance use deterioration during the study. Symptoms will be monitored closely throughout the trial to assess for deterioration. Any participant demonstrating gross clinical deterioration will be discontinued from the trial and appropriate intervention will be arranged. The rescue measures will include withdrawal from the study, immediate assessment by the PI or physician Co-I for a comprehensive psychiatric and substance abuse evaluation and determination of appropriate intervention, as well as emergency therapy sessions if the participant does not meet criteria for withdrawal from the study. In the case that the participant is aged 14-17, the PI will contact the parent/guardian to discuss the clinical deterioration and enlist involvement with proposed intervention. The intervention may include outpatient, day treatment, partial hospitalization, or inpatient treatment in the Medical University of South Carolina Institute of Psychiatry. These programs have highly trained clinicians competent in treating all psychiatric and substance use disorders. The PI holds admitting privileges for all of these clinical programs, allowing for efficient referral and management.

Referral for Participants Needing Continuing Treatment

At the end of the study, if a participant (or parent/guardian, as applicable) requires or requests continuing

Pro00014398

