2.2 Protection Against Risk

2.2.1 Adverse events related to study medication

The informed consent process will be used to thoroughly educate participants and parents/guardians about potential medication-related risks (including neuropsychiatric adverse events). This discussion will include thorough review of the FDA "black box" warning for varenicline, and clear communication that varenicline's use in adolescents is investigational. Rigorous screening procedures and strict exclusion criteria are designed to exclude potential participants at elevated risk for adverse events. This includes comprehensive psychiatric assessment and evaluation to exclude individuals with any lifetime history of mood disorder, psychotic disorder, suicidality, homicidality, or clinically significant hostility/aggression. The study medical clinician (physician or physician assistant, directly supervised by the PI, a board certified child & adolescent psychiatrist) will conduct serial psychiatric and medical evaluations weekly throughout treatment, providing comprehensive, detailed adverse event monitoring (see Section C3e). Additionally, vital signs and validated ratings of depression, anxiety, and suicidality symptoms (in light of caution around potential psychiatric adverse events) will be collected and reviewed at each visit. Participants and parents/guardians will have access to the study medical clinician 24 hours, 7 days a week for emergencies. Participants experiencing intolerable adverse events will have the opportunity to reduce dose or discontinue medication altogether, while remaining in the study for ongoing monitoring. The PI has admitting privileges for a full spectrum of psychiatric treatment services, including outpatient, day treatment, partial hospitalization, and inpatient programs, in the event that symptom acuity warrants intensive intervention. Urine pregnancy tests will be conducted weekly throughout treatment for female participants.

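### The plan does not provide for HADS and C-SSRS scores after a rescue withdrawal, and does not say whether the rescue rule or the intolerance rule governs a psychiatric adverse event

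*Combined protocol and SAP*

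**What the plan says.** Three places describe what happens when a participant gets worse.

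- **C3g, Clinical Deterioration Rescue Plan** (psychiatric or substance use deterioration): "Any participant demonstrating gross clinical deterioration will be discontinued from the trial and appropriate intervention will be arranged". It continues: "The rescue measures will include withdrawal from the study, immediate assessment by the PI or physician Co-I". The same sentence offers "emergency therapy sessions if the participant does not meet criteria for withdrawal from the study". Those criteria are not defined.
- **C3d, Pharmacological Intervention** (intolerable medication-related effects that persist on a reduced dose): "medication will be discontinued, and the participant will be encouraged to remain in the study for monitoring and non-medication study procedures".
- **Human Subjects section 2.2.1**: "Participants experiencing intolerable adverse events will have the opportunity to reduce dose or discontinue medication altogether, while remaining in the study for ongoing monitoring". Section C3e treats a positive pregnancy test similarly: medication stops and continued participation is encouraged.

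On data after termination, C3g (Study Termination) says: "If a participant is terminated for any reason, attempts will be made to continue collecting adverse event and smoking data over the 12-week treatment trial". This runs on through follow-up. HADS and C-SSRS are not named.

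Section C3e gives both scales at all visits. C3f (Safety: Secondary Analysis) will compare "depression/anxiety (HADS) and suicidality (C-SSRS) ratings using one-sided 2-sample t-tests". It names no visit, no summary of the repeated scores and no handling of missing scores. The only missing-visit rule in C3f concerns abstinence.

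**The concern.** HADS and C-SSRS are collected at study visits. Someone withdrawn under the rescue plan has no further planned visits, and the data still sought do not include these scales. Scores would then be missing because the participant's psychiatric state had worsened, which is the quantity the scales are meant to compare. If deterioration is commoner on varenicline, a comparison at a late visit omits more bad scores from that arm and moves toward no difference, the reassuring direction. The protocol gives the boxed warning and psychiatric monitoring great weight, so this is a poor place for outcome-dependent loss.

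The overlap between the rules adds to the problem. Two participants with the same psychiatric adverse event could be handled under different rules, one staying on the visit schedule and the other leaving it.

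**Working it through.** **1. Do the rules overlap?** The triggers differ: gross psychiatric or substance use deterioration in one, intolerable adverse effects in the other. C3d includes neuropsychiatric effects in the tolerability assessment, so an intolerable psychiatric adverse event can also be a gross deterioration. For that class of case one rule removes the participant from the trial and the other retains them. Nothing gives precedence. Elsewhere the rules do not conflict.

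**2. Which data survive a rescue withdrawal?**

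| Data | Provision |
|---|---|
| Scores up to and at the visit where deterioration is found | On record (scales given at all visits) |
| Later adverse events and smoking data | Attempts to collect (C3g) |
| Reason for termination | Counted and compared between arms by chi-square (C3g) |
| Later HADS and C-SSRS | Not provided for |

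**3. What does the t-test use?** C3f does not say. A worst post-baseline value keeps the trigger-visit score. A comparison at Week 12 does not.

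**4. The plan's own figures.** C3f gives no power, SD or expected rate for HADS, C-SSRS or deterioration. Its nearest safety figure is the 16.7% margin for treatment-emergent adverse events, with 166 participants, a 75% rate and 80% power. With 83 per arm and one-sided 5%:

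(1.645 + 0.842) × √(2 × 0.75 × 0.25 / 83) = 0.167

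The figure reproduces, but it concerns adverse event rates and says nothing about the scales.

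**5. Illustration; every input except 83 per arm is assumed.** Participants without rescue have equal means and SD 1 in both arms. Rescued participants score k SD worse at the late visit, with k from 2 to 4. There are rV rescued on varenicline and rP on placebo.

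- Difference with all scores kept: d = k × (rV − rP) / 83.
- Variance in an arm with r rescued: 1 + (r/83)(1 − r/83)k², averaged over the arms.
- Power: two-sample test, one-sided 5%.

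| rV vs rP | d (SD), k = 2 to 4 | Power, all scores kept | d if later scores are absent |
|---|---|---|---|
| 1 vs 0 | 0.02 to 0.05 | 7 to 9% | 0 |
| 3 vs 1 | 0.05 to 0.10 | 9 to 13% | 0 |
| 5 vs 1 | 0.10 to 0.19 | 14 to 26% | 0 |
| 8 vs 2 | 0.14 to 0.29 | 21 to 39% | 0 |

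For example, 5 vs 1 with k = 4 gives 4 × 4/83 = 0.19. In HADS points, if 4 vs 1 deteriorate with a lasting 9-point rise, (4 − 1) × 9/83 = 0.33 points would be observed as 0.

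The direction follows from the mechanism once deterioration is commoner on varenicline. The size depends entirely on the assumptions. Power is low even with complete scores.

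**The case against.** The strongest reply is that the plan captures the deterioration by other routes. The event that triggers rescue would itself be recorded as an adverse event, adverse event collection is attempted after termination for any reason, and reasons for termination are compared by arm. This stands: only the scale comparisons are exposed. It is also fair that few cases are likely, since lifetime mood or psychotic disorder and suicidality are excluded, and that later scores would partly reflect rescue care, so a lasting difference is not assured.

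A reader might infer more than the documents support.

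- **That the scores stop.** The text neither stops nor continues HADS and C-SSRS after withdrawal. Scores up to the trigger visit are kept, and whether the comparison loses information depends on the unstated time point.
- **That the psychiatric safety comparison as a whole loses these participants.** The neuropsychiatric adverse event test has a follow-up provision; the scale t-tests do not.
- **That the rescue paragraph contradicts itself.** It can be read as withdrawing gross cases and offering emergency therapy to lesser ones. The criteria are undefined, which is a different fault.
- **That a withdrawn quitter is scored as smoking because urine is not named.** Smoking data are sought expressly for the intent-to-treat analysis, whose endpoint is cotinine-verified, so cotinine is naturally included. Counting missed visits as non-abstinent applies to everyone.

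What remains is the missing provision for the two scales, the missing time point and missing-score rule, and the unresolved overlap.

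**Conclusion.** The point holds within these limits. Followed as written, the plan leaves HADS and C-SSRS scores after a rescue withdrawal uncollected or to chance, and it does not say how the t-tests treat their absence. A late-visit comparison is then biased toward no difference if deterioration is commoner on varenicline. The documents give no deterioration rate or scale SD, so the size is unknown. On the assumed inputs it is 0.02 to 0.29 SD, small enough that restoring the scores would seldom change the test result. The reasons to act are the direction of the bias, the safety value of the individual later scores and the low cost. Confidence is high in the omission and the overlap, and low in any figure for the bias.

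**What to change.** 1. Reconcile C3d, the C3g rescue plan and Human Subjects section 2.2.1 so that it is clear which governs a psychiatric adverse event that meets both rules. Record stopping study medication, receiving rescue care and leaving the study as separate events, each with its date. When medication stops and what care is given remain clinical decisions; no rule is proposed here.
2. In the C3g sentence on data after termination, keep the wording that attempts will be made and extend the list to adverse event, HADS, C-SSRS and smoking data, where feasible and unless consent for data collection is withdrawn.
3. In C3f, include all randomised participants in the HADS and C-SSRS comparisons. Use all available scores, including the trigger visit and later ones, and state the time point or summary (for example, worst post-baseline value or a repeated-measures model) and the handling of missing scores.

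The cost is some protocol wording and a few extra contacts, with instruments already in use. Some participants will decline, and later scores will partly reflect rescue care, which the recorded dates allow the report to show.

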1.2 Sources of Materials

Research materials obtained from participants include responses to questionnaires, psychiatric and physical examination results, urine tests (cotinine, drug metabolites, and pregnancy), and expired air carbon monoxide breathalyzer tests. Materials will be obtained specifically for research purposes. There will be no use of existing specimens, records, or data. Every effort will be made to maintain participant confidentiality, in accordance with HIPAA.

1.3 Potential Risks

Questionnaires and interviews are all non-invasive and, as such, involve minimal physical risk to participants. Potential risks incurred by participants include:

1. Adverse events related to study medication
2. Loss of confidentiality

1.3.1 Adverse events related to study medication

The varenicline package insert (http://www.pfizer.com/files/products/uspi_chantix.pdf) details adverse events associated with the medication. Specifically, it reports that “the most common adverse reactions (>5% and twice the rate seen in placebo-treated patients) were nausea, abnormal (e.g., vivid, unusual, or strange) dreams, constipation, flatulence, and vomiting.”

Meta-analyses of the four main adverse events in varenicline versus placebo groups in adult trials yielded relative risks (RRs) of 3.21 (95% CI 2.71, 3.80) for nausea, 1.50 (95% CI 1.26, 1.79) for insomnia, 2.79 (95% CI 2.09, 3.72) for abnormal dreams, and 1.20 (95% CI 1.00, 1.45) for headache (85). Similarly, adverse events in our adolescent pilot cessation trial included insomnia (4/15 participants) nausea (3/15 participants), and headache (3/15 participants) (27). No other adverse events were reported by more than one participant (including abnormal dreams – 1/15 participants). In a 2-week adolescent varenicline pharmacokinetic study, the most common adverse events were nausea, headache, vomiting, and dizziness (26).

While post-marketing anecdotal reports of psychiatric adverse events (32,33) led to an FDA “black box” warning for varenicline, a meta-analysis of controlled varenicline trials in adults (total $n=3091$ randomized to varenicline) yielded no significant increase, relative to placebo, in any psychiatric adverse events aside from sleep disturbance (see **Table 2** in Section A) (34). Additionally, a “real world” primary care cohort study including 10,973 smokers prescribed varenicline revealed no evidence of increased risk of self-harm, compared with smokers prescribed other cessation pharmacotherapies (35). The 2-week adolescent pharmacokinetic study by Faessel and colleagues (26) revealed 2 participants with sleep disturbances and 1 with a brief, mild episode of anger/irritability (out of 57 participants taking varenicline). Our adolescent pilot data similarly did not reveal psychiatric adverse events with any notable frequency. We are nonetheless, especially in light of regulatory and public caution surrounding varenicline, committed to excluding potentially vulnerable individuals (i.e., those with any lifetime history of mood or psychotic disorders, suicidality, or clinically significant hostility/aggression) and providing detailed, rigorous monitoring and management of potential psychiatric adverse events enrolled participants.

1.3.2 Loss of confidentiality

Any communication of personal information carries the potential risk of breach of confidentiality.

2. Adequacy of Protection Against Risks

2.1 Recruitment and Informed Consent

Recruitment of the participants will be from clinics, schools, and the community. The Medical University of South Carolina (MUSC) Institutional Review Board (IRB) approved Informed Consent (IC) will be obtained prior to the initial assessment. The consent will be explained orally and in the written form, and will be documented by the signature of the participant on the IC. For participants under 18 years old, a parent/legal guardian will provide consent and the participant will provide assent. The consent document will contain a thorough review of potential risks associated with trial participation, including potential medication-related risks (i.e., neuropsychiatric adverse events). Details of varenicline’s “black box” warning status will be provided to participants and parents/legal guardians, and will be discussed at length.

For re-consenting purposes for those participants under 18 years of age whose parent/legal guardian is not available to attend a study visit, we would conduct the re-consent process over the phone. We understand the importance of parental/guardian presence in the initial consenting procedures of study participation due to the seriousness of study medication (i.e. black box warnings). The issue that may arise, however, is that it may become intrusive and demanding for them to return for a re-consent need when in most cases the IC revisions are very minor and more editorial and administrative in nature. We would not want their child’s study participation to potentially negatively impact the parent/guardian’s employment, nor do we want such a need to be a barrier in the child’s study participation.

The process that study personnel would follow includes: Discussion with the parent/guardian by trained/approved study personnel would be completed prior to the next scheduled visit where a re-consent is to take place. When possible, study personnel will have forwarded the new ICF (electronically or hard copy) to the parent so he/she they could have the document in front of him/her

Pro00014398

during the re-consent discussion. Study personnel would clearly document the conversation and detailing the changes in the ICF. If the parent/legal guardian expresses understanding of the study changes and approves the child's continued participation and the ICF is available to the parent/legal guardian, he/she will sign and date the ICF accordingly, returning it for the minor's assent and study personnel's signature at the subsequent visit. If the parent/legal guardian does not have access to the ICF at the time, then the document will be sent home with the minor after their next completed study visit where the assent and staff's signature was obtained. The parent will sign the form accordingly and it will be returned to the study site at the following study visit. A copy of the fully signed document would be provided to the parent/legal guardian either by hardcopy (postal mail or minor's delivery) or electronically (email or fax) per the parent/legal guardian's preferred method. If the parent/legal guardian does not feel comfortable with the changes, requesting to have additional in person discussion with study personnel, then the minor's next visit would be cancelled/rescheduled for a date when the parent/legal guardian is able to attend the visit. At that time, routine in person consenting procedures would occur.

Absence of Coercion: Participation in the study is voluntary. Participants will be compensated \$40 for the initial assessment. The informed consent agreement that will be read to each volunteer (and parent/guardian as applicable) prior to enrollment in the study explains the following:

- a) Compensation is supplied at each study visit.
- b) Participants may discontinue participation in the study at any point.
- c) Withdrawing from the study will not result in any adverse consequences to the participants.

